### **8.2.2. Missing data handling for safety data**

For categorical variables, subjects with missing data are not included in calculations of percentages unless otherwise specified. When relevant, the number of subjects with missing data is presented.

#### **8.2.2.1. Missing/Partial dates in adverse events and concomitant medications/therapies**

##### **8.2.2.1.1. Missing start date**

###### *Missing day only*

- If the month and year are the same as the month and year of the first dose date, the day of first dose date will be used.
- If the month/year is before the month/year of the first dose date, the last day of the month will be used.
- If the month/year are after the month/year of the first dose date, the 01 will be used.

###### *Missing day and month*

- If the year is the same as the year of the first dose date, the first dose date will be used.
- If the year is prior to the year of the first dose date, December 31 will be used.
- If the year is after the year of the first dose date, January 1st will be used.

*Missing day, month, and year*

- No imputation can be done.

After missing date were imputed for an AE, if the AE is not the first record in a series of events for the same AE, and the imputed date is earlier than the start date of the previous record, then use the start date of the previous record instead.

**8.2.2.1.2. Missing end date***Missing day only*

- The last day of the month will be assigned as the missing day.

*Missing day and month*

- December 31 will be assigned to the missing fields.

*Missing day, month, and year*

- The event will be regarded as ongoing and the date cannot be imputed.

Unless the status of the end is ongoing, all the imputed dates will be compared against the End of Study date, death date, and data cut-off date. The earliest one will be used.

**8.2.2.2. Missing/Partial Dates at Screening Visits**

The following rules apply to dates recorded during the screening visits (e.g., prior anticancer therapy).

*Missing day only*

- The first day of the month will be used.

*Missing day and month*

- If the year is the same as the year of the earliest inform consent date at screening, the 1st of January will be used.
- If the year is before the year of the earliest inform consent date at screening, the 15th of June will be used.

*Missing day, month and year*

- No imputation can be done.

If the imputed end date is before the start date, the start date will be used as the end date. If the imputed dates are after the inform consent date at screening, then the inform consent date will be chosen.

**8.2.2.3. Missing/Partial Dates in Exposure**

No imputation will be done for the date of the first dose of study drug.

If the date of the last dose of study drug is missing or partially missing, it will be imputed as follows:

- If the last date of study drug is completely missing and there is no End of Treatment Disposition eCRF page for the study drug AND there is no death date, the subject should be considered to be ongoing and the data cutoff date for the analysis will be used as the last dosing date.
- If the last date of study drug is completely or partially missing and there is EITHER an End of Treatment eCRF page for the study drug OR a death date (on or before the data cutoff date), then the imputed last dose date is:
  - Last day of the year, if only the year is available and Year < Year of min(EOT date, death date).
  - Last day of the month, if both the year and month are available and Year = Year of min(EOT date, death date) and Month < Month of min(EOT date, death date).
  - min(EOT date, death date), for all other cases.

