4.1.2. Investigation schedule

Table (4.1.2) 1 describes the efficacy, safety and other assessments performed during the study.

Pre-screening or screening for IDH1m will occur at a central laboratory using either the most recent banked tumor sample (preferably from within the last 3 years) or a fresh biopsy. Subjects will undergo Screening procedures to determine eligibility within 28 days prior to the start of study treatment on C1D1, with the exception of baseline radiographic scans, which should be performed within 21 days prior to C1D1. Subjects are to attend study center visits as outlined in the Schedule of Assessments.

Study center visits will be conducted on an outpatient basis whenever possible. Subjects are to remain at the study center for 6 hours following the C1D1 and C2D1 doses for PK/PD and ECG assessments Table (4.1.2) 2. After the Screening Visit, a symptom-directed, limited physical exam should be performed at each Cycle, Day 1 visit, per institution standards of care.

An EOT Visit will be conducted as soon as possible after discontinuing study treatment (within 5 days of last dose of study treatment, if study drug dosing has not been delayed); in addition, subjects are to attend a Follow-up Visit 28 days (no more than 33 days) after the last dose of study treatment for final safety assessments. If a subject's dose is held and it is subsequently decided to discontinue treatment, the EOT Visit should be conducted as soon as possible, within 28 days (and no more than 33 days) after the last dose of study drug.

OS follow-up assessments will occur approximately every 12 weeks after EOT unless the subject is in PFS follow-up at that time. If a subject progresses or does not come back for scans while in PFS follow-up, then the OS follow-up assessments will begin at the next planned OS follow-up time point, following the schedule of every 12 weeks. OS follow-up will assess survival status and documentation of receipt and type of subsequent anticancer therapy unless consent to participate is withdrawn. If a subject begins a new anticancer therapy during PFS follow-up, information on the new therapy will need to be entered. OS follow-up will continue until all subjects have died, withdrawn consent, or are lost to follow-up, up to 24 months after the last subject enrolled, whichever occurs first. HRQOL (until the start of new anticancer therapy) assessments will be collected every 12 weeks after EOT.

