5.2. Exclusion criteria

Participants are excluded from the study if any of the following criteria apply:

14. Received a prior IDH inhibitor.
15. Received systemic anticancer therapy or an investigational agent < 2 weeks prior to C1D1 (washout from prior immune based anticancer therapy is 4 weeks). In addition, the first dose of study treatment should not occur before a period \geq 5 half-lives of the investigational agent have elapsed.
16. Received radiotherapy to metastatic sites of disease < 2 weeks prior to Day 1.
17. Underwent hepatic radiation, chemoembolization, and radiofrequency ablation < 4 weeks prior to C1D1.

18. Have known symptomatic brain metastases requiring steroids. Subjects with previously diagnosed brain metastases are eligible if they have completed their treatment and have recovered from the acute effects of radiation therapy or surgery prior to study entry, have discontinued corticosteroid treatment for these metastases for at least 4 weeks and have radiographically stable disease for at least 3 months prior to study entry. Note: up to 10 mg per day of prednisone equivalent will be allowed.
19. Have a history of another primary cancer, with the exception of: a) curatively resected nonmelanoma skin cancer; b) curatively treated cervical carcinoma in situ; or c) other primary solid or liquid tumor with no known active disease present that, in the opinion of the Investigator, will not affect subject outcome in the setting of current cholangiocarcinoma diagnosis.
20. Underwent major surgery within 4 weeks of C1D1 or have not recovered from post-surgery toxicities.
21. Pregnancy, possibility of becoming pregnant during the study and breast-feeding women or woman who plans to restart breast-feeding after the IMP administration/intake. Note: In the case where the Investigator has assessed that the subject may be pregnant as a result of medical interview, etc, the subject will be excluded.
22. Are taking known strong cytochrome P450 (CYP) 3A4 inducers or sensitive CYP3A4 substrate medications with a narrow therapeutic window ([Appendix 6](#)), unless they can be transferred to other medications within \geq 5 half-lives prior to dosing.
23. Have an active infection requiring systemic anti-infective therapy or with an unexplained fever $> 38.5^{\circ}\text{C}$ within 7 days of Day 1 (at the discretion of the Investigator, subjects with tumor fever may be enrolled).
24. Have any known hypersensitivity to any of the components of ivosidenib.

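### SAP 8.2.2.3 leaves a gap for partial last-dose dates: when the month is known and EOT or death falls in a later calendar year, the imputed date contradicts the recorded month

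*SAP*

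**What the plan says.** SAP 8.2.2.3 covers a missing or partial last-dose date when there is an End of Treatment page or a death date on or before the cutoff. It has three branches:

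1. Year only: "Last day of the year, if only the year is available and Year < Year of min(EOT date, death date").
2. Year and month: "Last day of the month, if both the year and month are available and Year = Year of min(EOT date, death date"), with the further condition that the recorded month is earlier than the month of that date.
3. Everything else: "min(EOT date, death date), for all other cases".

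Nothing elsewhere in the SAP overrides these branches.

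For the companion point, SAP 8.2.2.2 states its scope as "The following rules apply to dates recorded during the screening visits (e.g., prior anticancer therapy"). If only the day is missing, "The first day of the month will be used". A cap follows: "If the imputed dates are after the inform consent date at screening, then the inform consent date will be chosen".

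**The concern.** A partial-date rule should keep what was recorded and fill in only what is missing. Branch 2 does so within a calendar year but not across New Year. A record with a known month and an earlier year has too much information for branch 1 and the wrong year for branch 2. It is therefore given the EOT or death date, in a month when the record says dosing had already stopped.

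The last-dose date feeds several outputs:

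- treatment duration and dose intensity (SAP 5.2.1);
- the treatment-emergent window and the duration-adjusted event rates (SAP 5.4.1);
- the concomitant-medication window (SAP 5.2.2.4);
- the on-treatment death count (SAP 5.4.1, analysis of deaths).

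With about 10 subjects, one wrong date is one tenth of every such summary. A programmer who codes the SAP as written will reproduce the error.

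**Working it through.** The plan states no figure to reproduce, so the check applies the branches literally to worked dates.

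**Inputs.** The three branches are those of SAP 8.2.2.3. Protocol 4.1.1 and Table (4.1.2) 1 allow the EOT visit 5 to 33 days after the last dose. Protocol 4.1.2 says within 5 days if dosing was not delayed, and up to 33 days if a dose was held and treatment then stopped.

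**Last dose.**

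| Recorded | Earlier of EOT and death | Branch | SAP result | Latest date the record allows | Excess |
|---|---|---|---|---|---|
| Nov 2024 | 10 Dec 2024 | 2 | 30 Nov 2024 | 30 Nov 2024 | 0 days |
| 2024 only | 10 Jan 2025 | 1 | 31 Dec 2024 | 31 Dec 2024 | 0 days |
| Dec 2024 | 10 Jan 2025 | 3 | 10 Jan 2025 | 31 Dec 2024 | 10 days |
| Dec 2024 | 20 Jan 2025 | 3 | 20 Jan 2025 | 31 Dec 2024 | 20 days |
| Dec 2024 | 2 Feb 2025 | 3 | 2 Feb 2025 | 31 Dec 2024 | 33 days |
| Nov 2024 | 15 Mar 2025 (death, no EOT page) | 3 | 15 Mar 2025 | 30 Nov 2024 | 105 days |

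Rows 2 and 3 show that this is an oversight: knowing the month gives a worse date than not knowing it.

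**How often the gap is reached.** Take every true last-dose day in 2024 (366) and every gap to EOT from 0 to 33 days (34), with the day missing: 366 × 34 = 12,444 combinations. The imputed date leaves the recorded month in 561 of them: 558 in December and 3 in late November. December has 31 × 34 = 1,054 combinations, so its share is 558/1,054 = 53%. Equal weighting of days and gaps is an assumption, so these shares are illustrative.

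**Effect on relative dose intensity.** Assume 60 days of full dosing ending on 31 December, with the day not recorded. The relative intensity is then 60/(60 + excess):

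- excess 5 days: 60/65 = 92%;
- excess 20 days: 60/80 = 75%;
- excess 33 days: 60/93 = 65%.

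The true value is 100%.

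**Companion point.** The cap acts on a date with a known month only if the first of that month is after consent. Consent then lies in an earlier month, so the capped date always contradicts the record. For example, April 2024 with consent on 25 March 2024 becomes 1 April and is then moved to 25 March. In an enumeration over every consent day in 2024, with therapy ending from 400 days before to 14 days after consent, the cap acted on 1,260 dates with only the day missing. It contradicted the month in all 1,260. It never acted on year-only dates.

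Whether this can arise depends on when consent is taken. Protocol 5.2 excludes subjects who "Received systemic anticancer therapy or an investigational agent < 2 weeks prior to C1D1", and Protocol 4.1.2 says "Subjects will undergo Screening procedures to determine eligibility within 28 days prior to the start of study treatment on C1D1". For a month-only end date to show a 14-day washout, C1D1 must be at least 14 days after the month ends. With consent before the month starts and a month of at least 28 days, consent precedes C1D1 by at least 28 + 14 = 42 days. That is outside a 28-day window, but possible under the one-step consent at pre-screening that Protocol 9.1.1 permits.

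**The case against.** The strongest reply is that this seldom happens. Both rules act only on partial dates, and the dosing diaries and tablet returns in Protocol 6.4 should make an incomplete last-dose date uncommon. A reader might infer that any December last dose becomes a January date; the SAP does not say that, and complete dates are untouched.

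The larger figures also need several conditions at once. The SAP does not say whether the EOT date is the visit date. If it is, an undelayed visit falls within 5 days of the last dose, and the 33-day gap arises typically after a held dose. Protocol 6.1.1 also defines EOT, for a toxicity hold that is never restarted, as the date the drug was first held, which leaves almost no gap. The 65% figure is therefore a worst case. Equally, 33 days is not a ceiling when only a later death date is available.

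The safety effect is limited. Under Protocol 8.8.1, all-cause events are collected for only 28 to 33 days after the last dose, and later only related serious events, so a longer window can draw in few extra events. Deaths are more exposed: if the death date becomes the last-dose date, the death counts as on-treatment automatically. The SAP also tabulates all deaths, which softens this.

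A reader might infer that the primary result is at risk. The only route is indirect. SAP 8.2.1.1 uses the last dosing date as a floor for imputed starts of new anticancer therapy, which can enter PFS censoring, and that needs two partial dates in one subject.

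A reader might also infer that prior-therapy end dates are routinely moved back by weeks or months. The documents do not support that. The cap needs a missing day and a recorded month later than the consent month. For immune-based therapy the 4-week washout rules it out when consent is inside the 28-day window. No document gives the interval between one-step consent and C1D1, so the shift cannot be sized.

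These replies limit the size of the problem. None of them closes the gap in the branches.

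**Conclusion.** The last-dose rule is wrong as written, in a narrow and easily cured way. It needs a missing day, a known month and year, and an EOT or death date in a later calendar year; December to January is the typical case. On the visit-date reading of EOT, the imputed date is up to 33 days past the end of the recorded month. With only a later death date there is no fixed bound; 105 days in the example. The consequences are an overstated treatment duration, an understated relative dose intensity, and extended treatment-emergent, concomitant-medication and on-treatment-death windows for that subject. The primary test is not directly affected.

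The consent cap is a minor secondary defect. Its logic contradicts the recorded month whenever it acts on a date with a known month, but this is plausible mainly with one-step consent. It affects only the descriptive duration of the last prior line (SAP 5.2.2.1).

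**What to change.** In SAP 8.2.2.3, reword the second branch so that it assigns the last day of the recorded month whenever year and month are both known and that year-month is earlier than the year-month of the earlier of the EOT and death dates. Leave the other branches as they are. December 2024 with EOT on 20 January 2025 then gives 31 December 2024, and the contradictions in the enumeration fall from 561 to 0. Stating whether the EOT date is the visit date would also help.

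In SAP 8.2.2.2, cap imputed prior-therapy dates at the day before C1D1 instead of at consent, and do not let the cap move a date outside its recorded month.

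The cost is two lines of SAP wording and the matching code. No data collection or design element changes.

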### 8.3. Appendix C: EORTC QLQ-C30 and QLQ-BIL21 scales and scores

Table (8.3) 1 – EORTC QLQ-C30

	Number of Items	Item Range	Version 3.0 Item Numbers
Global health status	2	6	29, 30
Functional scales			
Physical functioning	5	3	1 to 5
Role functioning	2	3	6, 7
Emotional functioning	4	3	21 to 24
Cognitive functioning	2	3	20, 25
Social functioning	2	3	26, 27
Symptom scales			
Fatigue	3	3	10, 12, 18
Nausea and vomiting	2	3	14, 15
Pain	2	3	9, 19
Dyspnoea	1	3	8
Insomnia	1	3	11
Appetite loss	1	3	13
Constipation	1	3	16
Diarrhoea	1	3	17
Financial difficulties	1	3	28

Note: Item range is the difference between the possible maximum and minimum response to individual items; most items take values from 1 to 4, giving range = 3.

Table (8.3) 2 – EORTC QLQ-BIL21

	Number of Items	Item Range	Item Numbers
Eating symptoms	4	3	31 to 34
Jaundice symptoms	3	3	35 to 37
Tiredness	3	3	38 to 40
Pain symptoms	4	3	41 to 44
Anxiety symptoms	4	3	45 to 48
Treatment side-effects	1	3	49
Difficulties with drainage bag/tubes	1	3	50
Concerns regarding weight loss	1	3	51

Note: Item range is the difference between the possible maximum and minimum response to individual items; most items take values from 1 to 4, giving range = 3.

For all scales, the RS (Raw Score) is the mean of the component items:

$$RS = \frac{\sum_{i=1}^n I_i}{n}$$

Then for Functional scales:

$$Score = \left( 1 - \frac{(RS - 1)}{range} \right) \times 100$$

Where range is the possible maximum and minimum response to each item. E.g. an item scales from 1 to 4, thus range = 3.

## CL2-95031-008 - Statistical Analysis Plan | VV-TMF-169574 | 1.0

IvosidenibCL2-95031-008 - Statistical Analysis Plan - Final version 1.0

And for other scales:

$$Score = \frac{RS - 1}{range} \times 100$$
